7.5.1.2 Adverse Events Per 100 Patient-Years

In order to adjust for differences in subjects' durations in the study and the potential differential dropout rates between the preceding studies, TEAEs per 100 patient-years (PYs) will be calculated as follows:

Definition 1:

TEAEs per $100 \text{ PYs} = 100 \times \text{(Number of subjects who had at least 1 incidence / Total PYs)}$ Total PYs will be calculated by summing individual subjects' durations.

If subjects had at least 1 predefined AE, then the duration of these subjects are summed as from initial dose up to first incidence of predefined AEs.

If subjects had no predefined AE, then the duration of these subjects are summed as from initial dose through follow-up. Summed duration will be divided by 365.25 to represent per year.

Definition 2:

TEAEs per 100 PYs = $100 \times (Number of TEAEs for all subjects/ Total PYs)$

For number of TEAEs for all subjects, multiple occurrences of the same TEAE in the same subject will be counted multiple times.

Total PYs will be calculated by summing subjects' durations in this study through the follow-up period. Each subject's duration will be calculated as: (last date of follow-up in the study – date of initial dose of study drug + 1) / 365.25.

The number of TEAEs and TEAEs per 100 PYs will be provided by Definition 2, for all TEAEs (if analyzable) by SOC and PT for each preceding study, and Total.

Patient-Year analysis for following specified AE will also be conducted by Definition 1 with 95% confidence interval.

- Serious Infections
- Malignancies
- Herpes Zoster Related Disease (Herpes Zoster and Varicella)
- Herpes Zoster
- o Varicella
- Infections That Require Intravenous Anti-infectious Therapy

Note: Definition will be provided in 10.8 Appendix 8: AE of Special Interest.

Confidence Interval for TEAEs per 100 patient-years will be calculated for AE of special Interest based on following formula (assuming Poisson distribution).

- Upper limit of CI (TEAEs per 100 PYs): $100 \times \exp(\log(A/T) + Z_{(alpha)} * \sqrt{1/A})$
- Lower limit of CI (TEAEs per 100 PYs) : $100 \times \exp(\log(A/T) Z_{(alpha)} * \sqrt{1/A})$

A: Number of subjects who had at least 1 incidence

T: Total PYs

Z_(alpha): alpha % point of standard normal distribution

alpha = 0.025

TEAE of special interest per 100 patient-years analysis will be displayed the following category.

- \circ 0 6 months
- \circ 6 <- 12 months
- o 12 <- 24 months
- o 24 <- 36 months
- o 36 <- 48 months
- o 48 <- 60 months
- 60 <- 72 months
- o 72 <- 84 months
- o 84 months <

In addition, the subgroup analysis of Sex, Age Group, Concomitant Steroid at Baseline, Prednisone Dose at Baseline, Body Weight (kg) at Week 0, Concomitant DMARD category at Week 0, Maximum Dose of Study Drug and Study Region will be conducted.

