7 STATISTICAL METHODOLOGY

7.1 General Considerations

- For continuous variables, descriptive statistics will include the number of subjects (n), mean, standard deviation (SD), median, minimum, and maximum.
- For categorical variables: number and percentages of subjects will be described.
- For time-to-event variables: number and percentage of subjects with the event using Kaplan-Meier method, the cumulative event rate will be estimated and a plot will be constructed.
- All data processing, summarization, and analyses will be performed using SAS Drug Development (ver. 4.5), and PC-SAS (ver. 9.4) or higher versions.
- Specifications for table, figures, and data listing formats can be found in the TLF specifications for this study.
- For the definition of subgroups of interest can be referred to Section 7.8.
- Summaries based on FAS and SAF (e.g. disposition, baseline, efficacy data and safety data) will be presented by preceding studies and overall, unless specifically stated otherwise.
- Medical Dictionary for Regulatory Activities (MedDRA) 11.1 will be used as the coding dictionary for adverse event and medical history.
- Confidence interval for binary outcome is continuity corrected in all analysis.
- For the analyses of efficacy and pharmacodynamics variables in this extension study, values at the baseline in the preceding studies (RAJ1, RAJ3, and RAJ4) will be used as the baseline values. However, changes from baseline values of this extension study will also be examined where appropriate. For the analyses of safety, Week 0 of this extension study will be referred to as the baseline; however, changes from baseline values of the preceding studies (RAJ1, RAJ3, and RAJ4) will also be examined where appropriate.
- Change from baseline to post-baseline will be calculated as: post-baseline value baseline value. If the baseline value is missing, then that subject is not included in the calculation at any visit.
- Percent change from baseline to post-baseline will be calculated as: 100 × (change /baseline). If the baseline value is 0 or missing, or post-baseline value is missing, then percent change from baseline to post-baseline is missing.
- The values below the lower limit of quantitation (BQL) for β-D-glucan, hCG, Troponin, CK-MB will be treated as it is and these variables are not used for descriptive statistics

- and displayed in the listings. As for β -D-glucan, it is used for shift-from baseline analysis.

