TEAEs leading to death	X	X	X	preceding studies and overall
Most common TEAEs (> 5% in any preceding study)	X	X	X	preceding studies and overall
Most common serious TEAEs (> 5% in any preceding study)	X	X	X	preceding studies and overall
TEAEs excluding serious adverse events that equal to or exceed a threshold of 5% in any preceding study	X	X	X	preceding studies and overall
TEAEs of special interest Serious Infections Malignancies Herpes Zoster Related Disease (Herpes Zoster and Varicella) Herpes Zoster Varicella Infections That Require Intravenous Anti-infectious Therapy	X	х	х	preceding studies and overall
TEAEs by subgroups Sex (Male, Female,) Age Group at Week 0 (< 65 years, >= 65 years) Prior Anti-TNF DMARD Use in preceding study (User, Non-user) Prior Biologic DMARD-IR in preceding study (No, Yes) Duration of RA (years) in preceding study (< 5 years, >= 5 years) Number of Prior DMARDs Used in preceding study (0, 1, 2, >= 3) Number of Prior Biologic DMARDs Used in preceding study (0, 1, 2, >= 3) MTX Dose (mg/week) at Week 0 (None, 0 <- 8 mg/week, 8 <- 12	Х	X	X	preceding studies and overall

	Study for Analysis			Analysis Green
	RAJ1	RAJ3	RAJ4	Analysis Group
mg/week, > 12 mg/week)				
Concomitant Steroid at Week 0 (No, Yes)				
• Prednisone Dose (mg/day) at Week 0 (None, 0 <- 5 mg/day, > 5 mg/day)				
• Concomitant non-Biologic DMARD Use at Week 0 (No, Yes)				
Study Region (Japan, Korea, Taiwan)				
• Concomitant DMARD category at Week 0 (MTX, DMARD except				
for MTX only, None)				
TEAEs of special interest by subgroups				
• Sex (Male, Female,)				nraading
• Age Group at Week 0 (< 65 years, >= 65 years)	X	X	X	preceding studies and
• Concomitant Steroid at Week 0 (No, Yes)	Λ	Λ	Λ	overall
• Prednisone Dose (mg/day) at Week 0 (None, 0 <- 5 mg/day, > 5				Overan
mg/day)				

Patient-year analysis

	Study for Analysis			
	RAJ1	RAJ3	RAJ4	Analysis Group
TEAEs ^{1, 3}	X	X	X	preceding studies and overall
 TEAEs of special interest² Serious Infections Malignancies Herpes Zoster Related Disease (Herpes Zoster and Varicella) Herpes Zoster Varicella Infections That Require Intravenous Anti-infectious Therapy 	X	X	X	preceding studies and overall
 TEAEs of special interest by subgroups ² Sex (Male, Female,) Age Group at Week 0 (< 65 years, >= 65 years) Concomitant Steroid at Week 0 (No, Yes) Prednisone Dose (mg/day) at Week 0 (None, 0 <- 5 mg/day, > 5 mg/day) 	Х	X	X	preceding studies and overall

¹ According to Definition 2
² According to Definition 1

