³ Patient-years analysis will be displayed by time intervals and by overall period.

10.3 Appendix 3: Overview of Clinical Laboratory Evaluation, Vital Signs, and Electrocardiograms (ECGs) analyses

Table below summarizes the analyses of Clinical Laboratory Evaluation, Vital Signs, and Electrocardiograms (ECGs), with "X" indicating that the variable will be analyzed. All analyses will be based on the SAF and presented by preceding studies and overall, unless otherwise specified.

The overview of Clinical Laboratory Evaluation, Vital Signs, and Electrocardiograms (ECGs) analyses

	Study for Analysis				
	RAJ1	RAJ3	RAJ4	Analysis Group	
Clinical Laboratory Evaluation					
Quantitative Laboratory Test Results in SI Units, Hematology; Actual and Change from Week 0	X	X	X	preceding studies and overall	
Quantitative Laboratory Test Results in SI Units, Hematology; Actual and Change from Week 0 By study region	X	X	X	preceding studies and overall	
Quantitative Laboratory Test Results in SI Units, Biochemistry; Actual and Change from Week 0	X	X	X	preceding studies and overall	
Quantitative Laboratory Test Results in SI Units, Biochemistry; Actual and Change from Week 0 By study region	X	X	X	preceding studies and overall	
Quantitative Laboratory Test Results in SI Units, Urinalysis; Actual and Change from Week 0	X	X	X	preceding studies and overall	
Quantitative Laboratory Test Results in SI Units, Urinalysis; Actual and Change from Week 0 By study region	X	X	X	preceding studies and overall	
Quantitative Laboratory Test Results in SI Units, Fasting Lipids Profile; Actual and Change from Week 0	X	X	X	preceding studies and overall	
Quantitative Laboratory Test Results in SI Units, Fasting Lipids Profile; Actual and Change from Week 0 By study region	X	X	X	preceding studies and overall	
Quantitative Laboratory Test Results in SI Units, T-Chol/HDL, LDL/HDL Ratio; Actual and Change from Week 0	X	X	X	preceding studies and overall	
Quantitative Laboratory Test Results in SI Units, T-Chol/HDL, LDL/HDL Ratio; Actual and Change from Week 0 By study region	X	X	X	preceding studies and overall	
Quantitative Laboratory Test Results in SI Units, Erythrocyte Sedimentation Rate (ESR); Actual and Change from Week 0	X	X	Х	preceding studies and overall	
Quantitative Laboratory Test Results in SI Units, Erythrocyte; Actual and Change from Week 0 By study region	X	X	X	preceding studies and overall	

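### The 95% confidence interval formula for special-interest event rates has no value at zero events, and at small counts its lower limit lies above the exact Poisson limit

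*SAP*

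**What the plan says.** SAP section 7.5.1.2 defines two rates per 100 patient-years. Definition 1 divides the number of subjects with at least one event by patient-years counted up to the first event. Definition 2 counts every event.

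The six special-interest categories use Definition 1: serious infections, malignancies, herpes zoster and varicella combined, herpes zoster alone, varicella alone, and infections needing intravenous treatment. An interval is promised for them: "Patient-Year analysis for following specified AE will also be conducted by Definition 1 with 95% confidence interval".

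The method follows: "Confidence Interval for TEAEs per 100 patient-years will be calculated for AE of special Interest based on following formula (assuming Poisson distribution"). The limits are 100 × exp(log(A/T) ± Z√(1/A)), with alpha = 0.025 per tail.

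On how finely the rates are split, the SAP gives two accounts:

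- **Section 7.5.1.2** introduces nine time intervals with "TEAE of special interest per 100 patient-years analysis will be displayed the following category". It also lists eight subgroup factors, ending with "Concomitant DMARD category at Week 0, Maximum Dose of Study Drug and Study Region will be conducted".
- **Appendix 2 (section 10.2)** is narrower. Its footnote "Patient-years analysis will be displayed by time intervals and by overall period" is attached to the all-TEAE row only. Its row "TEAEs of special interest by subgroups" lists four factors: sex, age, steroid use and prednisone dose.

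**The concern.** The formula takes the logarithm of A and divides by A, so it fails at A = 0, and nothing in the SAP excludes that count. Two provisions might look like a fallback, but neither reaches this case. The rule in section 7.1, "Confidence interval for binary outcome is continuity corrected in all analysis", concerns binary outcomes, not person-time rates. The qualifier in "will be provided by Definition 2, for all TEAEs (if analyzable) by SOC and PT for each preceding study, and Total" belongs to the Definition 2 rates.

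This matters because, for a rare harm with no events, the upper limit is the result of interest: it says what rate the data exclude. A programmer following the SAP would have to leave the interval blank or improvise.

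There is also a small-count question. The formula is a large-sample approximation on the log scale, and some of these tables will hold counts of one, two or three.

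**Working it through.** **Inputs**

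- Per-tail alpha 0.025 (SAP 7.5.1.2). The two-sided level is 1 − 2 × 0.025 = 95%, as the SAP states, with Z = 1.96 read as the upper-tail point.
- 201 RAJ1 subjects in the extension and about 800 in total (SAP section 4).
- 0.55 malignancies per 100 patient-years: another JAK inhibitor's rate, from Protocol section 1.4, used here only as an assumed proxy.
- Mean follow-up of 1 to 3 years: an assumption, not a figure in the documents.

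**Formulas**, with limits as multiples of 100/T:

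- SAP: A × exp(±1.96/√A).
- Exact Poisson (Garwood): lower χ²(0.025; 2A)/2, upper χ²(0.975; 2A+2)/2.

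| A | SAP limits | Exact limits | Lower, SAP/exact | Upper, SAP/exact |
|---|---|---|---|---|
| 0 | undefined | 0 to 3.69 | – | – |
| 1 | 0.14 to 7.10 | 0.03 to 5.57 | 5.56 | 1.27 |
| 2 | 0.50 to 8.00 | 0.24 to 7.22 | 2.07 | 1.11 |
| 3 | 0.97 to 9.30 | 0.62 to 8.77 | 1.56 | 1.06 |
| 5 | 2.08 to 12.01 | 1.62 to 11.67 | 1.28 | 1.03 |
| 9 | 4.68 to 17.30 | 4.12 to 17.08 | 1.14 | 1.01 |

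**Tail probability at the SAP lower limit.** Under the SAP's own Poisson assumption, the chance of A or more events when the true mean equals the SAP lower limit should be 2.5%. It is 13.1%, 9.0% and 7.4% at A = 1, 2 and 3.

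**How often A = 0 occurs**, from P(0) = exp(−rate × patient-years):

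- *RAJ1, 0–6 months (section 7.5.1.2 reading).* With full follow-up, 201 × 0.5 = 100.5 patient-years. P(0) = exp(−0.0055 × 100.5) = 0.58, or 0.78 at 0.25 and 0.37 at 1.0 per 100 patient-years. Dropout would raise these. The exact upper limit is 100 × 3.689/100.5 = 3.67 per 100 patient-years.
- *RAJ1, overall period (narrower Appendix 2 reading).* At 0.55 per 100 patient-years and 1, 2 or 3 years of follow-up (201, 402 or 603 patient-years), P(0) = 0.33, 0.11 or 0.04.
- *Total, overall period.* 800 × 2 = 1,600 patient-years gives 1,600 × 0.0055 = 8.8 expected events and P(0) of about 0.00015. At A = 9 the lower limit is 14% and the upper limit 1% above exact.

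**Coverage**, averaged over a uniform grid of expected counts, for three rules:

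| Expected count | SAP as written (no interval at 0) | SAP plus exact limits at 0 only | Garwood |
|---|---|---|---|
| 0.05–1 | 34% | 95.4% | 98.9% |
| 1–5 | 87% | 96.0% | 98.0% |

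**The case against.** The strongest reply concedes the gap at zero and disputes the rest. The log-scale interval is a standard large-sample method. The 13.1%, 9.0% and 7.4% are one-sided tail probabilities, not coverage. If exact limits were supplied at A = 0 alone, average two-sided coverage would be about nominal, as the last table shows, while Garwood is over-conservative. On this view one sentence on zero events would do, and replacing the formula everywhere goes further than the defect. The same argument notes that the intervals are descriptive, that the zero-cell probabilities rest on a borrowed rate and on the wider reading of the SAP, and that the separate table specifications, which are not available here, may say how such cells are shown.

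Much of this is fair. It confirms that the zero-event gap is the main point and the small-count behaviour secondary. Average coverage does, however, hide local dips under the zero-rule version: to 86.9% near an expected count of 0.14, and to 93.1% within 1–5. A display convention in a table specification would also not supply the missing limit.

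A further caveat is that person-time stops at the first event, so T depends slightly on A. Garwood is therefore exact only under the working Poisson assumption. For rare events the difference is immaterial.

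**Conclusion.** The concern holds. The SAP promises an interval for every special-interest rate and prescribes a formula that cannot produce one at zero events, with no fallback in either document. Under section 7.5.1.2 such cells are to be expected: a 58% chance for RAJ1 malignancy at 0–6 months, with a range of 37% to 78% across assumed rates of 1.0 to 0.25 per 100 patient-years. Under the narrower Appendix 2 plan the RAJ1 overall-period chance is 4% to 33%, depending on assumed follow-up.

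The raised lower limit at counts of one to three is real but secondary, and the upper limit errs in the cautious direction. The reach is confined to sparse cells by interval, preceding study and subgroup. The overall malignancy rate is little affected, and no decision depends on any of these intervals. It should be corrected, but it does not threaten the study's conclusions.

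**What to change.** In section 7.5.1.2, replace the formula for every special-interest rate with the exact Poisson (Garwood) interval:

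- Lower limit: 100 × χ²(0.025; 2A)/(2T), set to 0 when A = 0.
- Upper limit: 100 × χ²(0.975; 2A+2)/(2T).

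This keeps the SAP's Poisson assumption and applies at every count. A minimal alternative is to keep the present formula and state exact limits for A = 0 only. That closes the main gap but leaves the lower limits at A = 1 to 3 as they are.

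The cost is one formula and no new data. The exact interval is conservative by construction (coverage at least 95% under the Poisson model), and lower limits in sparse cells will fall, for example from 0.14 to 0.03 × 100/T at A = 1.

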7.5.1.3 Subgroup Analyses

In order to assess whether or not AEs vary across specific patient groups, AE occurrence will be summarized by SOC and PT for the subgroups specified in Section 7.8.

7.5.2 Clinical Laboratory Evaluation

7.5.2.1 All Laboratory Tests

For clinical laboratory parameters (hematology, biochemistry, fasting lipid profile, and urinalysis), raw values at each scheduled visit, change from Week 0 at each post-Week 0 visit, shift from Week 0 and shift from reference range will be summarized using descriptive statistics or frequency tabulations. For Fasting Lipids Profile, all analysis will be conducted using the measured values which are confirmed under fasting condition. In addition, all Lipid

Profile values including non-fasting condition will also be summarized for descriptive statistics.

For subjects who shift from RAJ3, clinical laboratory test is conducted at central institution at each region (Japan, Korea, and Taiwan) in accordance with each procedure and each reagent for clinical test. The possibility of harmonization among each region was conducted before clinical laboratory test was initiated in Korea and Taiwan. If clinical laboratory evaluation could be harmonized, then these measurement data among each region could be regarded as the same scale. If harmonization was reported to be difficult, then clinical test would be summarized by Study Region (Japan, Korea, and Taiwan). However, among clinical laboratory tests not-harmonized, for exploratory analysis, Beta-D-glucan, Glucose, HCO3, urine pH, urine gravity will be summarized by whole population. Qualitative Urinalysis test will be summarized by Study Region, only (see 7.8.2 Subgroup analysis for Study Region (Japan, Korea, and Taiwan).

- Clinical laboratory tests harmonized
 - All of the hematology test
 - Biochemistry test except for Beta-D-glucan, Glucose, HCO3
 - All of the fasting lipid profile
 - CRP
- Clinical laboratory tests not-harmonized
 - Beta-D-glucan, Glucose, HCO3
 - All of the urinalysis test
 - * Pregnancy test, CPK monitoring, and Hepatitis test are not applicable to harmonization and it will be displayed in listing only.
- For continuous variables, descriptive statistics of raw values at each scheduled visit will be summarized at each time point using SI unit. For the ratio T-Chol to HDL and the ratio LDL to HDL, descriptive statistics will be summarized at each post-baseline visit.
- For continuous variables, descriptive statistics of change from Week 0 value will be summarized at each visit using SI unit.
- In addition, for the selected laboratory tests (hematology, biochemistry, fasting lipid profile), descriptive statistics of raw values and change from baseline of preceding study at each visit will be summarized similarly. In this analysis, time course of each safety variable will be presented from baseline of preceding study up to end of RAJ2 study by Treatment Sequence Set. Following analysis visits of preceding study will be used,
- Subjects shifted from RAJ1
 - o RAJ1 Week 0
 - o RAJ1 Week 12
 - Week 0 (RAJ1 Week 16)

- Subjects shifted from RAJ3/4
 - \circ RAJ3/4 Week 0
 - o RAJ3/4 Week 12
 - o RAJ3/4 Week 28
 - o RAJ3/4 Week 40
 - o RAJ3/4 Week 52
 - o Week 0
- Shift-from-Week 0 table: Shift from Week 0 to highest value, and Shift from Week 0 to lowest value during entire period, for all laboratory variables. If the laboratory value of same subject is measured lower from normal range at one visit, and higher from normal range at the other visit, that subject will be counted as both low and high from Week 0 during entire period.
- Graphical analysis:
 - The mean-standard deviation plot of actual values and changes from week 0 will be presented for the selected laboratory tests (hematology, biochemistry, fasting lipid profile).

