[Subjects who transferred from studies RAJ3 or RAJ4] Chest radiography is taken at the Week 0 visit, or data obtained within 28 days prior to the Week 0 visit may be used.  
If a respiratory AE is observed, a chest radiography may be taken at any time as necessary, even in an unscheduled visit.
- m. Blood samples for pharmacodynamics (lymphocyte subset assay) are collected before the first dose of the study drug on the day of the Week 0 visit.
- n. Assessment of disease activity: **Physician** – TJC (68 joints), SJC (66 joints), PGA (VAS); **Subject** – SGA (VAS), subject's assessment of pain (VAS), HAQ-DI, WPAI, and SF-36V2®.
- o. SF-36v2® is administered every 4 weeks until Week 48 and every 24 weeks after Week 48 to subjects from study RAJ1 and every 24 weeks throughout the study period to subjects from studies RAJ3 or RAJ4.
- p. WPAI is administered only to subjects who transferred from studies RAJ3 or RAJ4.
- q. AEs must be collected from the time of the administration of the first dose of study drug to the end of all assessments at the end of study (at time of follow-up).

- CONFIDENTIAL -

- r. After all of the assessments and tests scheduled for Week 0 have been completed, the subjects will receive the first dose of the study drug at each study center.
- s. [Subjects who transferred from study RAJ1] If the study is terminated before the Week 48 visit, the specified date for the study visit at the end of treatment will be the date of the previous visit + 28 days (allowable range,  $\pm 7$  days). If the study is terminated in or after the Week 48 visit, the specified date for the study visit at the end of treatment will be the date of the previous visit + 84 days (allowable range,  $\pm 14$  days).  
[Subjects who transferred from studies RAJ3 or RAJ4] The specified date for the study visit at the end of treatment will be the date of previous study visit + 84 days (allowable range,  $\pm 14$  days).
- t. For unscheduled visits, these assessments and tests should be performed only if clinically indicated as determined by the investigator.
- u. In principle, the subject should visit the study center on the specified date. If it is not possible for subjects to visit the study center on the specified date, the date of the visit should be adjusted to the date closest to the reference date as possible.
- v. Only subjects who transferred from study RAJ1 should make study visits at Weeks 2, 4, 8, 16, 20, 28, 32, 40, and 44.

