## **5.8 Total Amount of Blood**

The total amount of blood drawn for samples will differ from subject to subject in this study because duration of participation in the study will differ depending upon the subject.

The volume of blood drawn per sample and the total annual sample volume are shown in the table below. In addition, blood samples are collected for ESR determination performed at each study center; the volume will differ from center to center (approximately 1 to 2 mL per sample). See Table 1, Schedule of Assessments, for details regarding the blood-sampling schedule.

Blood samples will be taken at other times as necessary to follow up on laboratory test values obtained.

- CONFIDENTIAL -

[Subjects who transferred from RAJ1]

Assessment	Volume of sample	Total annual sample volume (No. of draws)	
		First year	2nd year and later
Hematology	2 mL	28 mL (14 times)	8 mL (4 times)
Biochemistry (including CRP and lipid profile tests)	14 mL	196 mL (14 times)	56 mL (4 times)
Lymphocyte subsets	2 mL	4 mL (2 times)	2 mL (1 time)
Total	18 mL	228 mL	66 mL

[Subjects who transferred from RAJ3 or RAJ4]

Assessment	Volume of sample	Total annual sample volume (No. of draws)	
		First year	2nd year and later
Hematology	Japan: 2 mL Korea: 3 mL Taiwan: 3 mL	Japan: 10 mL (5 times) Korea: 15 mL (5 times) Taiwan: 15 mL (5 times)	Japan: 8 mL (4 times) Korea: 12 mL (4 times) Taiwan: 12 mL (4 times)
Biochemistry (including CRP and lipid profile tests)	Japan: 14 mL Korea: 15.5 mL Taiwan: 13.5 mL	Japan: 70 mL (5 times) Korea: 77.5 mL (5 times) Taiwan: 67.5 mL (5 times)	Japan: 56 mL (4 times) Korea: 62 mL (4 times) Taiwan: 54 mL (4 times)
Lymphocyte subsets	Japan: 2 mL Korea: 3 mL Taiwan: 3 mL	Japan: 4 mL (2 times) Korea: 6 mL (2 times) Taiwan: 6 mL (2 times)	Japan: 2 mL (1 time) Korea: 3 mL (1 time) Taiwan: 3 mL (1 time)
Total	Japan: 18 mL Korea: 21.5 mL Taiwan: 19.5 mL	Japan: 84 mL Korea: 98.5 mL Taiwan: 88.5 mL	Japan: 66 mL Korea: 77 mL Taiwan: 69 mL

\* Additional 5 mL of blood per sample needs to be drawn in Japan and Taiwan, and 8.5 mL in Korea at the scheduled visits after initiation of study drug administration if HBV-DNA assay is performed.

\* Additional 4 mL of blood per sample needs to be drawn in Japan, and 5 mL in Korea and Taiwan if determination of CK-MB, troponin T, and aldolase is performed.

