**APPENDIX <2>: LABORATORY TESTS**

	Visit*	Collecting tube (unique to Japan**)	Parameters to be analyzed
Hematology	[Subjects who transferred from RAJ1] Week 0, Week 2, Week 4, Week 8, Week 12, Week 16, Week 20, Week 24, Week 28, Week 32, Week 36, Week 40, Week 44, Week 48, Week 60, Week 72, Week 84, Week 96, Week 108, Week 120, Week 132/end of treatment/early termination, end of study (at time of follow-up), Unscheduled Visits [Subjects who transferred from RAJ3 or RAJ4] Week 0, Week 12, Week 24, Week 36, Week 48, Week 60, Week 72, Week 84, Week 96, Week 108, Week 120, Week 132/end of treatment/early termination, end of study (at time of follow-up), Unscheduled Visits	2 mL vacutainer tube containing EDTA-2K	Hemoglobin, hematocrit, RBC, WBC, differential WBC, platelet count
Biochemistry	[Subjects who transferred from RAJ1] Week 0, Week 2, Week 4, Week 8, Week 12, Week 16, Week 20, Week 24, Week 28, Week 32, Week 36, Week 40, Week 44, Week 48, Week 60, Week 72, Week 84, Week 96, Week 108, Week 120, Week 132/end of treatment/early termination, end of study (at time of follow-up), Unscheduled Visits [Subjects who transferred from RAJ3 or RAJ4] Week 0, Week 12, Week 24, Week 36, Week 48, Week 60, Week 72, Week 84, Week 96, Week 108, Week 120, Week 132/end of treatment/early termination, end of study (at time of follow-up), Unscheduled Visits	9 mL vacutainer tube containing separating medium For glucose: 2 mL vacutainer tube containing NaF+EDTA-2Na For $\beta$ -D glucan: 3 mL container for blood endotoxin/ $\beta$ -D-glucan	Na, K, Ca, Cl, Mg, HCO 3 , BUN, phosphorus, glucose, creatinine, ALP, AST (GOT), ALT (GPT), $\gamma$ -GTP, TBL, total protein, albumin, uric acid, CPK, LDH, serum amylase, $\beta$ -D-glucan, eGFR
Biochemistry (during CPK monitoring)	At the time of CPK monitoring	4 mL vacutainer tube containing the separating medium	CK-MB, troponin T, aldolase

- CONFIDENTIAL -

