Acute phase reactants	[Subjects who transferred from RAJ1] Week 0, Week 2, Week 4, Week 8, Week 12, Week 24, Week 28, Week 32, Week 36, Week 40, Week 44, Week 48, Week 60, Week 72, Week 84, Week 96, Week 108, Week 120, Week 132/end of treatment/early termination, end of study (at time of follow-up), Unscheduled Visits [Subjects who transferred from RAJ3 or RAJ4] Week 0, Week 12, Week 24, Week 36, Week 48, Week 60, Week 72, Week 84, Week 96, Week 108, Week 120, Week 132/end of treatment/early termination, end of study (at time of follow-up), Unscheduled Visits	(Included among biochemistry tests)	CRP
		In-hospital testing	ESR
Pharmacodynamics	Week 0, Week 48, Week 96 /end of treatment/early termination, end of study (at time of follow-up), Unscheduled Visits	2 mL vacutainer tube containing EDTA-2K	Lymphocyte subsets

\* Necessary hospital visits will differ from subject to subject because the duration of participation in this study will differ depending upon the subject. After Week 132, tests will be performed every 12 weeks (only the pharmacodynamics tests will be performed every 48 weeks after Week 96.)

\*\* Types of collecting tube used at Korea and Taiwan are described in the laboratory handling manual.

- CONFIDENTIAL -

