7.5.2.4 Liver Abnormalities

Each categories are mutually exclusive.

The following potentially clinically significant criteria in liver function tests for Alkaline Phosphatase (ALP), Alanine Transaminase (ALT), total bilirubin, Aspartate Transaminase (AST) and their combination are defined. The subject's highest value during the investigational period will be used.

Parameter	Criteria
ALT	> 3xULN
	> 5xULN
	> 10xULN
	> 20xULN
AST	> 3xULN
	> 5xULN
	> 10xULN
	> 20xULN
ALT or AST	> 3xULN

> 8xULN

Total Bilirubin > 2xULN

ALP > 1.5xULN

ALT and/or AST OR Total Bilirubin(*) (ALT and/or AST \geq 3xULN) or

total bilirubin > 2xULN

ALT and/or AST AND Total Bilirubin^(*) (ALT and/or AST > 3xULN) and total bilirubin

> 2xULN

The number and percentage of subjects with potentially clinically significant values in liver function tests during the investigational period will be presented.

Additionally, confirmed liver abnormities will be characterized as moderate and marked, as follow:

Moderate: ALT or AST $> 3 \times ULN$ OR Total Bilirubin $> 2 \times ULN$.

Marked: ALT or AST $> 3 \times ULN$ AND Total Bilirubin $> 2 \times ULN$.

Number and percentage of subjects in each category at each scheduled visit will be summarized. These combinations of elevated values are based on measured value within the same sample.

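### Worst-value laboratory tables set preceding studies side by side although RAJ1 has 13 scheduled draws by Week 48 and RAJ3/RAJ4 have 4, so the columns are not comparable

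*SAP*

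**What the plan says.** **Worst-value rules.** SAP 7.5.2.1 specifies "Shift from Week 0 to highest value, and Shift from Week 0 to lowest value during entire period" for all laboratory variables. SAP 7.5.2.2 tabulates the shift to the worst CTCAE value and 7.5.2.3 places each subject's highest or lowest value in reference ranges, both over the whole period. For the liver criteria in 7.5.2.4 the subject's "highest value during the investigational period will be used", and the plots in 7.5.2.5 use study maxima. The laboratory window table in SAP 7.11.6 puts no time limit on the on-treatment minimum and maximum.

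**Presentation.** SAP Appendix 3 covers these displays with the same sentence that Appendix 2 uses for adverse events: "All analyses will be based on the SAF and presented by preceding studies and overall".

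**Schedule.** Note v to Protocol Table 1 reads: "Only subjects who transferred from study RAJ1 should make study visits at Weeks 2, 4, 8, 16, 20, 28, 32, 40, and 44". Protocol Appendix 2 accordingly lists laboratory visits for RAJ1 that begin "Week 0, Week 2, Week 4, Week 8, Week 12, Week 16, Week 20, Week 24" and continue every 4 weeks to Week 48. The list for RAJ3 and RAJ4 begins "Week 0, Week 12, Week 24, Week 36, Week 48, Week 60". From Week 48 both lists run at 12-week steps to Week 132, and then "After Week 132, tests will be performed every 12 weeks".

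**Acknowledgement.** SAP 7.11.4 notes the two schedules but uses them only to decide which by-visit time points apply to whom. Nothing limits the search for the extreme to shared visits, reports the number of draws, or warns about reading across columns.

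**The concern.** The maximum of more measurements is at least as large as the maximum of fewer. If two groups have the same risk of an abnormal value at each draw, the more often sampled group shows more subjects with one.

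The RAJ1 column also differs from the other two in starting dose, background DMARD or MTX treatment and entry criteria. A reader who sees a different rate of high CPK or low neutrophils could attribute it to any of these, when part of it comes from how often blood was taken. The artefact could equally hide a real difference. The Total column mixes the two detection intensities.

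The issue matters most for short-lived abnormalities. Protocol 1.3 describes most CPK increases in RAJ1 as transient, and Protocol 1.4 describes the neutrophil decreases as reversible. Monitoring can amplify the gap: CPK and liver elevations trigger retests (Protocol 5.4.4.1 and 5.4.4.2), more scheduled draws find more triggers, and the SAP does not exclude retest values from the extremes.

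**Working it through.** **1. Draw counts.** RAJ1 scheduled draws after Week 0, to Week 48: Weeks 2, 4, 8, 12, 16, 20, 24, 28, 32, 36, 40, 44, 48 = 13. Removing the nine RAJ1-only visits leaves Weeks 12, 24, 36, 48 = 4.

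Check against Protocol 5.8, which counts Week 0: 13 + 1 = 14 and 4 + 1 = 5 first-year draws, as printed. The Japanese volumes also agree: hematology 2 × 14 = 28 mL and 2 × 5 = 10 mL; biochemistry 14 × 14 = 196 mL and 14 × 5 = 70 mL.

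**2. Later follow-up.** To week W after Week 48, at equal follow-up, the counts are 13 + (W − 48)/12 and 4 + (W − 48)/12. End-of-treatment, follow-up and unscheduled draws are left out.

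| To week | RAJ1 | RAJ3/RAJ4 | Ratio |
|---|---|---|---|
| 48 | 13 | 4 | 3.25 |
| 132 | 20 | 11 | 1.82 |
| 360 | 39 | 30 | 1.30 |

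**3. Episodes caught by a scheduled draw.** Assume one abnormal episode of L weeks with onset uniform over Weeks 0 to 48. It is caught if onset falls within the L weeks before a draw.

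- L = 2: RAJ1 13 × 2 / 48 = 26/48 = 54%; RAJ3/RAJ4 4 × 2 / 48 = 8/48 = 17%.
- L = 4: RAJ1 100%, since no gap between draws exceeds 4 weeks; RAJ3/RAJ4 16/48 = 33%.
- L = 8: 100% and 32/48 = 67%.
- L = 12: 100% in both.

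Of the episodes that the RAJ1 schedule would catch, the other schedule misses 1 − 8/26 = 69%, 67% and 33% at 2, 4 and 8 weeks. The documents give no episode durations, so these lengths are assumptions.

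**4. Subjects with at least one abnormal value.** Assume risk p per draw, equal in all cohorts. With independent draws the probability is 1 − (1 − p)^n. At p = 1% by Week 48: 1 − 0.99^13 = 12.2% and 1 − 0.99^4 = 3.9%. For correlated draws, a normal latent value with a shared subject effect was used (correlation 0.8).

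| To week | p | Independent, RAJ1 vs RAJ3/RAJ4 | Correlation 0.8 |
|---|---|---|---|
| 48 | 0.5% | 6.3% vs 2.0% | 2.5% vs 1.3% |
| 48 | 1% | 12.2% vs 3.9% | 4.5% vs 2.5% |
| 48 | 2% | 23.1% vs 7.8% | 8.0% vs 4.7% |
| 132 | 1% | 18.2% vs 10.5% | 5.4% vs 4.1% |
| 360 | 1% | 32.4% vs 26.0% | 6.9% vs 6.3% |

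**5. What would cancel it.** With independent draws and p = 1% in RAJ3/RAJ4, the columns are equal if the RAJ1 per-draw risk is about 0.31 times as large by Week 48, or 0.77 times by Week 360.

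**6. Common visits only.** With the four shared visits to Week 48, both cohorts show 3.9% at p = 1%.

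**The case against.** A reader might infer that RAJ1 will show more laboratory toxicity. The documents do not support that. RAJ1 subjects start at 50 mg/day and the others at 100 mg/day (SAP 3.2). Protocol 3.3 also excluded RAJ1 subjects on hemoglobin, blood counts, transaminases, bilirubin, eGFR and CPK, with no such limits for RAJ3 or RAJ4. Both may push the other way. Only the statement at equal risk stands.

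A reader might also carry the threefold Week 48 gap over to the planned tables. Those cover the whole period, and SAP 7.3.1 has exposure categories beyond 84 months. The extra draws stop at Week 48, so the gap dilutes, and independent draws are the extreme case.

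The plan covers part of this already. By-visit summaries are unaffected, moderate and marked liver abnormalities are tabulated at each scheduled visit (SAP 7.5.2.4), and the laboratory analyses are descriptive in a non-randomised extension. These points limit the severity. They do not make the worst-value columns comparable, and the SAP does print them side by side. For adverse events, SAP 7.5.1.2 adds patient-year rates because duration and dropout may differ between preceding studies; the worst-value laboratory tables have no counterpart.

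Finally, restricting every table to common visits would do harm. Retests after CPK or liver elevations are where peaks and confirmations appear, and removing them from the Total would hide real extremes. Nor do common visits alone equalise the number of draws when follow-up differs by subject. Both objections stand, and the fix respects them.

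**Conclusion.** The concern holds in a limited form. The draw counts, the whole-period extremes and the side-by-side display are all in the documents. At equal per-draw risk, denser sampling inflates the RAJ1 column. Its size rests on assumptions about risk, correlation, episode length and equal follow-up: roughly a twofold to threefold ratio by Week 48 at 1% per draw (1.8 to 3.1), falling to 1.10 to 1.25 by Week 360. The direction of any observed difference cannot be predicted, because dose and entry criteria differ too. No hypothesis test is affected. Because long-term safety is a stated objective, a change to the SAP is still worthwhile.

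**What to change.** 1. Keep the all-data worst-value tables, including unscheduled values, for each preceding study and for the Total. Add a footnote giving the number of draws per subject by preceding study and stating that the columns are not comparable across preceding studies.

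2. Add to SAP 7.5.2.1 to 7.5.2.4, for example: *A supplementary table by preceding study takes the highest, lowest or worst value only from scheduled visits common to all cohorts (Weeks 12, 24, 36, 48 and every 12 weeks thereafter), within a common time horizon or the time intervals of Section 7.5.1.2. Any comparison between preceding studies uses this table.*

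3. Reconcile the reference-range table, which covers the whole period in SAP 7.5.2.3 but is titled as a by-visit table in Appendix 3.

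The cost is SAP wording, one visit filter and some extra tables; no new data are needed. If data lock has passed, SAP 1 allows the change to be justified in the study report. The common-visit version omits some real RAJ1 abnormalities, but these remain in the all-data tables.
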